7.8.6 Physical Examination

Physical exams will include assessment of the following body systems:

- General appearance
- Skin
- Lymph nodes
- Head, eyes, ear, nose, and throat
- Neck
- Thorax/lungs
- Cardiovascular
- Abdomen
- Musculoskeletal
- Neurological

Physical examination results (normal/abnormal) and details of abnormalities will be listed for each subject. For each physical examination body system, the number and

CONFIDENTIAL

Page 24 of 28

percentage of subjects with abnormalities will be summarized by treatment group and overall for each scheduled visit where the examination is performed.

7.8.7 Injection Site Reactions

Injection site inspections evaluate the occurrence, location, severity, and duration of the following reactions:

- Erythema/redness
- Pain/tenderness
- Induration/swelling
- Other sign/symptom

Severity evaluations (mild, moderate, severe) and duration evaluations (<3 days, 3 days to 1 week, >1 week to 1 month, >1 month) will be conducted at each inspection. Reactions will be listed for each injection for each subject by treatment group. The number and percentage of subjects with reactions of each severity and duration will be summarized by treatment group and overall for each scheduled visit where the inspection is performed.

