7.6.1 Adverse Events

An AE is any untoward medical occurrence [i.e., any unfavorable and unintended sign (including abnormal laboratory findings), symptom or disease] in a subject or clinical investigation subject after providing written informed consent for participation in the study until the EoS visit. Therefore, an AE may or may not be temporally or causally associated with the use of a medicinal (investigational) product.

In addition, all reports of intentional misuse and abuse of the study treatment are also considered an AE irrespective if a clinical event has occurred. See [Section 7.6.2](#) for an overview of the reporting requirements.

The occurrence of AEs must be sought by non-directive questioning of the subject at each visit during the study. AEs also may be detected when they are volunteered by the subject during or between visits or through physical examination finding, laboratory test finding, or other assessments.

Abnormal laboratory values or test results constitute AEs only if they fulfill at least one of the following criteria:

- they induce clinical signs or symptoms,
- they are considered clinically significant,
- they require therapy.

Clinically significant abnormal laboratory values or test results should be identified through a review of values outside of normal ranges/clinically notable ranges, significant changes from baseline or the previous visit, or values which are considered to be non-typical in healthy subjects. Investigators have the responsibility for managing the safety of individual subject and identifying AEs. Alert ranges for liver and kidney related events are included in [Appendix 1](#) and [Appendix 2](#), respectively. Additional clinically notable laboratory values are included in [Appendix 3](#).

AEs must be recorded on the AE CRF under the signs, symptoms or diagnosis associated with them, and accompanied by the following information:

1. Severity grade

- mild: usually transient in nature and generally not interfering with normal activities
- moderate: sufficiently discomforting to interfere with normal activities
- severe: prevents normal activities

2. Relationship to the study treatment

- Related
- Possibly related
- Not related

3. Duration (start and end dates) or if the event is ongoing an outcome of not recovered/not resolved must be reported.

4. Whether it constitutes a SAE (see [Section 7.6.2](#) for definition of SAE) and which seriousness criteria have been met

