12.4. Appendix 4 - Schedule of Assessments

Table 9: Schedule of Assessments

Period	Screening	Treatment							Washout / Follow-up			
Visit	1	2	3	4	5	6	7	8	9	10	TD	EoS
Day	-28 to -3	1 (predose)	11	31 (predose)	41	61 (predose)	71	91	101	121	-	170
Window			±2	±2	±3	±2	±3	±2	±3	±3		±10
Informed consent	X											
Medical history	X											
Drug & alcohol screen	X											
I/E criteria	X	X										
Physical Exam	X	X	X	X		X		X		X	X	X
Height	X											
Weight	X	X										X
Vital signs	X	X	X	X	X	X	X	X	X	X	X	X
12-lead ECG	X	X						X				X
HIV, Hepatitis B, Hepatitis C	X											
aPTT, Free and total FXI	X	X	X	X	X	X	X	X	X	X	X	X
aPTT (corrected for FXI), FXI:C		X				X		X				X
PK assessment: total MAA868		X	X	X	X	X	X	X	X	X		X
Antidrug antibodies (ADA)		X		X		X	X	X		X		X
Exploratory biomarker collection	X	X		X		X		X		X		
Complete safety Labs	X	X	X	X	X	X		X		X	X	X
Pregnancy test	Serum	Urine			Urine			Urine			Urine	Urine
Urine	X	X	X	X	X	X		X		X	X	X
Fecal occult blood test	X	X										
AE collection						X						
Concomitant meds						X						
Local assessment of CV and cerebrovascular events							X					
Local assessment of bleeding events							X					
Dispense Study Medications		X		X		X						
Drug Accountability		X		X		X		X				
MAA868		X		X		X						
Placebo		X		X		X						

Period	Screening	Treatment							Washout / Follow-up			
Visit	1	2	3	4	5	6	7	8	9	10	TD	EoS
Day	-28 to -3	1 (predose)	11	31 (predose)	41	61 (predose)	71	91	101	121	-	170
Window			±2	±2	±3	±2	±3	±2	±3	±3		±10
Injection site inspection (post-dose)		X	X	X	X	X	X					
Study disposition								X			X	X

TD = Study treatment discontinuation; EoS = End of Study; FXI:C = Factor XI coagulation activity

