The study is comprised of 3 periods: screening period, treatment period, and follow-up period. The screening period may last up to 4 weeks. The treatment period is 91 days and consists of 3 monthly subcutaneous doses of MAA868 (or matching placebo). Study drug is administered at the study site on day 1 (visit 2), day 31 (visit 4), and day 61 (visit 6). During the treatment period, subjects will return to the study site on day 11, day 31, day 41, day 61, day 71, and day 91 for safety assessments. The follow-up period is 79 days and continues to day 170, allowing a 110-day washout period from the last study drug administration. During the follow-up period, subjects will return to the study site on day 101, day 121, and day 170 (EoS) for additional safety evaluations.

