6.1 Time points and Visit Windows

Day 1 is defined as the day subjects receive the first dose of study drug. Relative days after Day 1 are calculated as (assessment date – Day 1 date) + 1. Relative days prior to Day 1 are calculated as (assessment date – Day 1 date). The day prior to Day 1 is Day -1.

Baseline is defined as the most recent result obtained prior to first administration of study medication. This occurs at visit 2 (day 1 pre-dose). If the assessment is not performed at visit 2, the value from visit 1 (screening) will be used. If this value is not present, there will be no baseline value.

Trough FXI levels will only be used if they are considered "on treatment". A measurement is considered "on treatment" if it is collected within 30 (± 5) days after the last administration of MAA868.

CONFIDENTIAL

Page 13 of 28

Statistical Analysis Plan

Sponsor Name: Anthos
Sponsor Protocol ID: ANT-004

Covance Study ID: 000000189471

All data will be analyzed using nominal study visits as defined in the schedule of assessments and eCRF. Unscheduled visits will be listed but not tabulated. No visit windows will be applied for summary and analysis.

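### SAP 7.8.7 tabulates injection-site reactions by visit only, so the table gives no count of subjects ever affected and follows the third injection for about 10 days

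*SAP*

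**What the plan says.** SAP 7.8.7 grades severity in three levels and duration in four: "duration evaluations (<3 days, 3 days to 1 week, >1 week to 1 month, >1 month) will be conducted at each inspection". The only tabulation is by visit: subjects with "reactions of each severity and duration will be summarized by treatment group and overall for each scheduled visit where the inspection is performed". Beside it stands a listing: "Reactions will be listed for each injection for each subject by treatment group".

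Protocol Table 9 (Appendix 4) schedules site inspections on Days 1, 11, 31, 41, 61 and 71. None is ticked for Days 91, 101 or 121, for treatment discontinuation or for end of study. Doses are given on Days 1, 31 and 61 (SAP 2.2). SAP 6.1 adds: "No visit windows will be applied for summary and analysis"; it also keeps unscheduled visits out of the tables.

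Adverse events run on a separate track. Under Protocol 7.6.1 they are collected "after providing written informed consent for participation in the study until the EoS visit", and the record must include "Duration (start and end dates) or if the event is ongoing an outcome of not recovered/not resolved must be reported".

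**The concern.** Protocol 1.2 says the incidence of injection-site reactions will be assessed, and SAP 3.2 lists them among the safety endpoints. For a repeated subcutaneous antibody, a reader will want to know how many subjects reacted, how severe the worst reaction was after each injection, and how long reactions lasted.

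The table described in SAP 7.8.7 is not built for the first question and serves the third unevenly. It has no row for any reaction across visits, no summary by injection, and no rule for a reaction seen at two visits or for several reaction types at one visit. The neighbouring sections do have a counting rule: adverse events (SAP 7.8.2), bleeding events (7.8.8) and cardiovascular and thromboembolic events (7.8.10) all count a subject once per category. The third injection, which follows the most prior exposure, is inspected for the shortest time.

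**Working it through.** The plan states no figure for this point, so there is none to reproduce.

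**1. Days from each dose to each inspection.** Elapsed time = inspection day − dose day. The range in brackets adds the Table 9 windows of the dosing visit and the inspection visit (±2 days for Days 11, 31 and 61; ±3 for Days 41 and 71; none for Day 1), taking each window from its nominal day.

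| Inspection | After dose 1 (Day 1) | After dose 2 (Day 31) | After dose 3 (Day 61) |
|---|---|---|---|
| Day 1 | 0 | – | – |
| Day 11 | 10 (8–12) | – | – |
| Day 31 | 30 (28–32) | 0 | – |
| Day 41 | 40 (37–43) | 10 (5–15) | – |
| Day 61 | 60 (58–62) | 30 (26–34) | 0 |
| Day 71 | 70 (67–73) | 40 (35–45) | 10 (5–15) |

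**2. Reachable duration categories, taking one month as 30 days.**
- Doses 1 and 2 are inspected to 70 and 40 days, so all four categories can occur.
- Dose 3 is inspected to 71 − 61 = 10 days, or 15 at the window limit. The category above one month cannot occur at any scheduled inspection. If the gap is only 5 to 7 days, the category from one week to one month cannot occur either.
- On a dosing day, a reaction at the new site can only be rated under 3 days.

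**3. One reaction at several visits.** Suppose duration is re-rated while a reaction is present. A 12-day reaction to dose 1 is under 3 days on Day 1 and between one week and one month on Day 11 (10 days elapsed). It then sits in different duration rows at two visits.

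**4. Mixed sites.** The table shows a fresh site beside a 30-day-old one on Day 31 (doses 2 and 1) and on Day 61 (doses 3 and 2). A row defined by visit does not separate them.

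**5. Subjects ever affected.** Given visit counts c₁ to c₆ among n subjects, the number ever affected lies between max(cᵢ) and min(n, Σcᵢ). With n = 12, the active arm of one cohort (Protocol 5.3), and illustrative counts:
- 2 at each visit: lower bound 2, upper bound min(12, 6 × 2) = 12, that is 16.7% to 100%.
- 1 at each visit: lower bound 1, upper bound min(12, 6 × 1) = 6, that is 8.3% to 50%.

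These bounds assume that the number affected at each visit is itself known. Without an any-reaction row or a rule for several reaction types, even that may not follow from the severity and duration rows.

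**6. Adverse event track.** Collection continues for 170 − 71 = 99 days after the last inspection.

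**The case against.** A reader might infer that the plan cannot show how long reactions last, or cannot show whether they worsen with repeat dosing. The documents do not support either reading. A duration category is recorded at every inspection, and the full range is observable for two of the three injections; the 10-day limit affects only dose-3 reactions still present on Day 71. Inspections also fall at matched times after each dose: post-dose on Days 1, 31 and 61, and 10 days later on Days 11, 41 and 71. Severity can therefore be compared across doses from the by-visit table, unless old reactions persist long enough to blur it.

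It can also be said that the missing count exists elsewhere. The listing is per injection and per subject, with 12 active subjects per cohort. Adverse event tables count a subject once per preferred term to end of study, with start and end dates behind them. This is a real mitigation, but a partial one. Neither document says that every inspection finding is entered as an adverse event, and the Amendment 2 summary speaks of clinically significant findings, so mild reactions may exist only in the inspection data. Skin is examined at Days 91 and 121 and at end of study, but SAP 7.8.6 reports that by body system, not by injection site.

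Three further points stand:
- The current Protocol 2.2 frames the secondary safety endpoint as adverse events; the SAP's wording follows protocol Version 2.0. Injection-site reactions do remain in the safety evaluation (Protocol 8.6).
- The case report form and table shells, not available here, may settle how an ongoing reaction is rated and which rows appear.
- The two earlier single-dose studies reported no injection-site reactions among 48 + 24 = 72 subjects on active drug (Protocol 1.1). If reactions stay that rare, the listing may suffice in practice.

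**Conclusion.** The point holds as a limited reporting gap. As written, the SAP 7.8.7 table gives no number of subjects with any reaction, can show a persisting reaction under different durations at successive visits, can mix fresh and 30-day-old sites on Days 31 and 61, and cannot show durations beyond about 10 days (at most 15) after the third dose. The gap lies more in the summary than in the data, apart from the short inspection period after dose 3.

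This rests on three assumptions: visit windows run from nominal days, one month is 30 days, and the table shells add no rows beyond those SAP 7.8.7 describes. The changing-category point further assumes that duration is re-rated while a reaction is present. The table is descriptive and no significance test depends on it; the primary endpoint is unaffected. The point is minor, but the correction is cheap enough to make.

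**What to change.** In SAP 7.8.7, add a summary by subject and by injection number (1, 2, 3), overall and by treatment group, with each reaction counted once:
- any reaction;
- maximum severity;
- last recorded duration, or ongoing at last inspection, using the adverse event end date where there is one.

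Keep the by-visit display as supportive. The cost is SAP wording and one added table. No new data are needed, because reactions are already to be listed by injection and subject.

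Optionally, if the schedule is being amended anyway, add a site inspection at the existing Day 91 visit, where a physical examination is already planned. Dose 3 would then have the same nominal 30-day look as doses 1 and 2 (91 − 61 = 30). This needs a written protocol amendment and its approvals (Protocol 10.1). At nominal Day 91 it does not by itself reach the category above one month, so the ongoing flag is needed either way.

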7.8.8 Bleeding Events

Subject counts and percentages and event counts for the number of treatment-emergent adjudicated bleeding events will be summarized by treatment group and overall. The definition of treatment-emergent can be found in [section 7.7.2](#). The following summaries will be presented:

- Major bleeding events
- Clinically relevant non-major bleeding events
- Nuisance (not clinically relevant) bleeding events
- No bleeding event

If a subject has more than one bleeding event in each above category, the subject will be counted only once in the tabulation. All adjudicated bleeding events will be listed.

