2.2. Secondary objectives and endpoints

Objective	Endpoint

 To evaluate the proportion of patients achieving FXI inhibition $\geq 50\%$, $\geq 80\%$, and $\geq 90\%$ at trough after the first and second dose (Day 31 and Day 61) at different dose levels of MAA868 	
 Occurrence of achieving $\geq 50\%$, $\geq 80\%$, and $\geq 90\%$ inhibition of FXI ($< 50\%$, $< 20\%$, or $< 10\%$ free FXI) at trough on Day 31 and Day 61 at different dose levels of MAA868

 To evaluate the safety and tolerability following multiple s.c. administration of MAA868 compared to placebo in patients with AF 	
 Occurrence of adverse events (AEs), including serious AEs (SAEs) during the Treatment Period and through EoS

 To evaluate the incidence of major bleeding events, clinically relevant non-major (CRNM) bleeding events and total bleeding with MAA868 relative to placebo during the treatment period 	
 Occurrence of confirmed major bleeding events, CRNM bleeding events and total bleeding events during the treatment period

 To evaluate the immunogenicity of MAA868 compared to placebo. 	
 Screening and confirmation for anti-drug (MAA868) antibodies (ADA)

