2.1 Study Objectives

- Primary:
 - To evaluate the proportion of subjects that achieve $\geq 50\%$, $\geq 80\%$, or $\geq 90\%$ Factor XI (FXI) inhibition at trough after the third dose (Day 91) at different dose levels of MAA868.
- Secondary:
 1. To evaluate the proportion of subjects achieving FXI inhibition $\geq 50\%$, $\geq 80\%$, and $\geq 90\%$ at trough after the first and second dose (Day 31 and Day 61) at different dose levels of MAA868.
 2. To evaluate the safety and tolerability following multiple s.c. administration of MAA868 compared to placebo in subjects with AF.
 3. To evaluate the incidence of major bleeding events, clinically relevant non-major bleeding events, and total bleeding with MAA868 relative to placebo during the treatment period.
 4. To evaluate the immunogenicity of MAA868 compared to placebo.
- Exploratory:
 1. To evaluate the effect of MAA868 compared to placebo on the incidence of major cardiovascular, cerebrovascular, and venous thromboembolic events.
 2. To evaluate the change from baseline in D-dimer and other thrombogenesis markers with MAA868 relative to placebo during the treatment period.

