3.2 Secondary Endpoints

Efficacy

- The proportion of subjects achieving $\geq 50\%$, $\geq 80\%$, or $\geq 90\%$ inhibition of FXI ($< 50\%$, $< 20\%$, or $< 10\%$ free FXI) at trough on Day 31 and Day 61 at different dose levels of MAA868.

Safety

- All safety assessment results during the treatment and follow-up periods. Safety endpoints include:
 - Adverse Events (AE)
 - Physical exam
 - Laboratory parameters
 - Vital Signs
 - Electrocardiogram (ECG)
 - Hypersensitivity reactions
 - Injection site reactions
- Occurrence of confirmed major bleeding events, clinically relevant non-major (CRNM) bleeding events, and total bleeding events during the treatment period.
- Identification of anti-drug (MAA868) antibodies using a ligand-binding assay.

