7.7.2 Secondary Efficacy Analysis

The secondary efficacy analysis is to evaluate the proportion of subjects achieving FXI inhibition $\geq 50\%$, $\geq 80\%$, and $\geq 90\%$ at trough after the first and second dose (Day 31 and Day 61) at 3 dose levels of MAA868. The analyses described for the primary endpoint will be repeated for the secondary efficacy variables as follows:

- Cohort 1 (MAA868 120 mg monthly or placebo): at Day 31 and 61.
- Cohort 2 (MAA868 180 mg monthly or placebo): at Day 31 and 61
- Cohort 3 (MAA868 TBD mg monthly or placebo): at Day 31 and 61

No comparisons to the placebo or statistical tests will be conducted for the primary efficacy endpoint.

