7.8.2 Adverse Events (AE)

All AEs recorded on the eCRF will be coded using the MedDRA dictionary version 22.0. Treatment-emergent Adverse Events (TEAEs) will be of primary interest and are defined as:

- AEs with a start date on or after the date of first dose of study drug and up to the EoS visit
- AEs with start date prior to the date of first dose of study drug whose severity worsens on or after the date of first dose of study drug

TEAEs will be summarized by system organ class (SOC) and preferred term (PT) by treatment group and overall. Subject counts and percentages and event counts will be presented for the following TEAE summaries:

- All TEAEs
- Serious TEAEs
- All TEAEs by severity
- All TEAEs by relationship to study drug
- TEAEs potentially related to study drug
- TEAEs potentially related to study drug by severity
- TEAEs leading to discontinuation of study drug
- TEAEs leading to withdrawal from study

A subject will only be counted once per SOC and once per PT. If a subject reports more than one AE with the same PT, the AE with the maximum severity will be presented. AE severity grades are mild, moderate, or severe. An AEs relationship to study drug is assessed as related, possibly related, or not related.

If the start date/time of an AE is incomplete or missing, the AE will be assumed to be a TEAE, unless the incomplete start date/time or the end date/time indicates an AE started prior to the start of the infusion. AEs with missing causality are assumed

Statistical Analysis Plan

Sponsor Name: Anthos

Sponsor Protocol ID: ANT-004

Covance Study ID: 000000189471

to be related. If the severity of an AE is missing, the AE will be counted under the maximum severity possible.

Listings will be presented by subject for TEAEs, AESIs, serious AEs (SAEs), AEs leading to discontinuation of study drug, and AEs resulting in death.

No statistical comparisons of AEs between treatment groups will be performed.

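### SAP 7.8.8 does not tabulate the secondary bleeding endpoint: as best read, its window runs to Day 170 instead of the 91-day treatment period, and it has no subject-level total

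*SAP*

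**What the plan says.** Protocol 2.2 defines the endpoint as "Occurrence of confirmed major bleeding events, CRNM bleeding events and total bleeding events during the treatment period". SAP 3.2 repeats it ("clinically relevant non-major (CRNM) bleeding events, and total bleeding events during the treatment period"), and the objective in SAP 2.1 refers to "total bleeding with MAA868 relative to placebo during the treatment period". On timing, SAP 2.2 says "The treatment period is 91 days" and then "The follow-up period is 79 days and continues to day 170".

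The analysis section reads differently. SAP 7.8.8 states: "Subject counts and percentages and event counts for the number of treatment-emergent adjudicated bleeding events will be summarized by treatment group and overall". For the meaning of treatment-emergent it sends the reader to section 7.7.2, which opens with "The secondary efficacy analysis is to evaluate the proportion of subjects achieving FXI inhibition" and does not define the term. The definition is in 7.8.2: "AEs with a start date on or after the date of first dose of study drug and up to the EoS visit". The summaries listed in 7.8.8 are major, CRNM, nuisance and no bleeding event, and a subject is counted once within each category.

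Protocol 8.6 (Bleeding Events) asks for yes/no tabulations of major, CRNM and total bleeding, plus an on-treatment composite of major and/or CRNM bleeding. SAP section 8 declares that nothing has changed from the protocol's planned analyses.

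**The concern.** Bleeding relative to placebo during treatment is a named secondary objective of a study meant to support dose selection for phase 3. The analysis section should produce the quantity that the endpoint section defines, and it does not. Its window is longer, and the total is absent.

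The restriction to the treatment period looks deliberate. In the same protocol table, adverse events are to be collected over the treatment period and on to the end of study, while bleeding is limited to the treatment period.

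If the SAP is followed literally, treatment-period bleeds are pooled with follow-up bleeds and no subject-level total is specified. Anyone wanting the subject-level endpoint would have to rebuild it from the listing. Because section 8 declares no changes, the departure is not flagged where a reader would look for it.

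**Working it through.** The plan gives no expected bleeding rate or power figure for this endpoint. The check is therefore day arithmetic and a comparison of the rows.

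**Inputs**
- Treatment period: 91 days. Follow-up: 79 days, to Day 170 (SAP 2.2). The plan's figures agree: 91 + 79 = 170.
- Visit windows (protocol Table 9): Day 91 ±2, end of study ±10.
- Doses on Days 1, 31 and 61 (protocol 3.1 and Table 9).
- Half-life 20 to 28 days (protocol 3.2).
- 12 active subjects per cohort (protocol 5.3).

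**Step 1: window.** Taken literally, the pointer to 7.7.2 leaves the window undefined. The only definition in the SAP gives first dose to end of study. Neither is the endpoint's window. On the second reading:
- Share of counted days after Day 91: (170 − 91)/170 = 79/170 = 46%.
- Lowest, with end of study on Day 160 and the Day 91 visit on Day 93: (160 − 93)/160 = 67/160 = 42%.
- Highest, with end of study on Day 180 and the Day 91 visit on Day 89: (180 − 89)/180 = 91/180 = 51%.
- In elapsed days from Day 1: 79/169 = 47%, and 169/90 = 1.88 times the endpoint's time.

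These are shares of time. As an illustration only, assume a constant bleeding hazard. A 10% subject incidence by Day 91 would then become 1 − 0.90^(169/90) = 18.0% by Day 170, and 5% would become 9.2%.

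**Step 2: total row.** A subject may appear in several categories. The number with any bleed therefore lies between the largest row and the sum of the rows. With assumed counts in a 12-subject arm of 0 major, 2 CRNM and 4 nuisance:
- Lower bound: max(0, 2, 4) = 4, or 4/12 = 33%.
- Upper bound: 0 + 2 + 4 = 6, or 6/12 = 50%.

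The no-bleeding row does not help. Under protocol 7.6 and Appendix 5 it is an adjudication outcome for a suspected event, not a count of subjects free of bleeding.

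**Step 3: does another passage close the gap?** SAP Table 1 says only that bleeding endpoints are tabulated by treatment group. It gives no window and no total. The word overall in 7.8.8 follows treatment group and matches the all-subjects column of Table 1. It does not mean a sum over bleeding categories.

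**Step 4: is it a version effect?** SAP section 1 names protocol Version 2.0 as its source. That version has the same treatment-period endpoint (2.2), and the same total row and composite (8.6.2). The gap does not come from Amendment 2.

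**Step 5: can the protocol 8.6 window stand in for the treatment period?** That window ends 30 days after the last dose. Against 91 days:

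| Doses received | Last dose | Window ends | Days missed |
|---|---|---|---|
| 1 | Day 1 | Day 31 | 60/91 = 66% |
| 2 | Day 31 | Day 61 | 30/91 = 33% |
| 3 | Day 61 | Day 91 | 0 |

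The two coincide only for subjects who complete on schedule. The 8.6 wording is also conditional on early discontinuation, and it places the third dose on Day 91 while protocol 3.1 and Table 9 place it on Day 61. Those passages must be reconciled.

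**Step 6: is the longer window useless?** No. Ignoring absorption delay, the share of the third dose remaining 30 days later is 2^(−30/20) = 0.35 to 2^(−30/28) = 0.48. A through-end-of-study summary is worth keeping, but it is not this endpoint.

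**The case against.** Several points can be made for the plan.
- **Event totals.** SAP 7.8.8 promises event counts, and each event receives one adjudicated category. Total events can therefore be added from the major, CRNM and nuisance rows. That is correct, but the sum still covers the period to Day 170 and gives no subject-level incidence.
- **Table shells.** Table 1 refers to shells that are not among the documents, and a total row or a period split might be there. That is possible, but it would not cure SAP text that conflicts with its own endpoint definition.
- **The window is inferred.** The Day 170 reading goes through a broken pointer. It is the only definition available, and the literal alternative is no window at all.
- **Protocol 8.6.** The protocol has its own on-treatment rule for early discontinuers, so how they are handled is the sponsor's to settle. That stands, which is why the fix asks for reconciliation and a separate table. The endpoint wording still supports a treatment-period table.
- **Little is at stake numerically.** The analysis is descriptive, both arms are counted over the same window, no bias in the comparison has been shown, and all adjudicated bleeds are listed. All of that is true. It limits the severity, but the table still reports a different quantity.

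**Conclusion.** The concern holds and should be fixed. Followed exactly, SAP 7.8.8 does not report the bleeding endpoint that protocol 2.2 and SAP 3.2 define. About 46% of the days counted (42% to 51% with visit windows) fall after the treatment period, and subject-level total bleeding cannot be derived from the listed rows. SAP section 8 does not disclose either difference.

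This rests on reading treatment-emergent as 7.8.2 defines it, there being no other definition in the SAP. The effect on the observed bleeding rates is unknown, because the documents give no rate for this population. No data are lost.

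The missing on-treatment major/CRNM composite is a separate departure, from the protocol's analysis section and not from either endpoint definition. A smaller parallel is SAP 7.8.10, which omits the on-treatment thromboembolic composite of protocol 8.6, although counting those events to end of study is consistent with the exploratory endpoint.

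**What to change.** In SAP 7.8.8:
1. Make the secondary-endpoint table cover first dose to the Day 91 visit for all subjects. State the cut-off for subjects with no Day 91 visit, and how interrupted or restarted dosing (protocol 5.6) is handled.
2. Add two subject-level rows: total bleeding (major, CRNM or nuisance, excluding events adjudicated as no bleeding) and major or CRNM bleeding.
3. Present the protocol 8.6 on-treatment analysis separately, once the sponsor has reconciled its window wording with the dosing schedule. It should not replace item 1.
4. Keep the through-end-of-study summary as an additional, clearly labelled table.
5. Correct the pointer from 7.7.2 to 7.8.2, and list any remaining difference from the protocol in SAP section 8.

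The cost is SAP wording, one further table and two rows, all from adjudicated data already collected. Reconciling the protocol 8.6 wording is a separate task for the sponsor.
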